10.7 Definition of the End of Trial

The trial end will be when the last CADISS patient (number 250) has had their last visit.

10.8 Discontinuation/withdrawal of participants and stopping rules

10.8.1 Withdrawal procedure, treatment suspension and 'stopping rule(s)'

Patients will only be withdrawn from the study if consent is withdrawn. In this circumstance no follow-up data will be collected.

If a patient is randomised and later imaging shows that there is no dissection, the patient should still have all follow-up visits and calls as this is an intention to treat study.

11: IMPs and non-IMPs used in the trial

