6.2 Dosage regimen and rationale

At randomisation, patients will be randomised to either antiplatelets or anticoagulants. The treatment the patient receives will be at the discretion of the prescribing physician and will reflect the treatment options outlined in protocol section 3.2. This drug treatment will continue until the three month follow-up appointment unless the medication of choice needs to be stopped for safety reasons. Following the three month period the patient should be continued on whatever treatment the prescribing physician feels is best for the patient in question.

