9.1 Informed consent

Informed consent will be obtained by the Principal Investigator and/or a nominated deputy as recorded on Sponsor's Delegation of Responsibilities Log. Only those members of the study team who have clinical responsibility for the care of patients under the care of the general medical service will be permitted to undertake informed consent. All individuals taking informed consent will have received training in Good Clinical Practice (GCP).

Consent to enter this study will be obtained after a full account has been provided of its nature, purpose, risks, burdens and potential benefits, and the patient has had the opportunity to deliberate. The patient will be allowed to specify the time they wish to spend deliberating, usually up to 24 hours.

Periods shorter than 24 hours will be permitted if the patient feels that further deliberation will not lead to a change in their decision, and provided the person seeking consent is satisfied that the patient has fully retained, understood and deliberated on the information given. This provision has been made with the support of our patient advisory group.

Likewise, periods longer than 24 hours will be permitted should the patient request this. The Investigator or designee will explain that the patients are under no obligation to enter the trial and that they can withdraw at any time during the trial, without having to give a reason.

A copy of the signed Informed Consent Form (ICF) along with a copy of the most recent approved Patient Information Sheet (PIS) will be given to the study participant. The original signed consent form will be retained at the study site (one filed in the medical notes and one filed in the TMF). A copy of the consent form will also be given to the patient.

If new safety information results in significant changes to the risk–benefit assessment, the consent form will be reviewed and updated if necessary. All subjects, including those already being treated, will be informed of the new information, given a copy of the revised consent form and asked to re-consent if they choose to continue in the study.

A witnessed consent form can be used in cases where the patient has understood the study and its relative risks but is unable to provide written consent *i.e.* dysphasia.

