In cases where potential participants are deemed incompetent to make a decision during the acute phase following their stroke, advice will be sought from a relative or carer. The relative or carer will be provided with the information sheet for relatives and carers outlining their role and also the requirements of the participant in the study. The relative or carer will be encouraged to ask questions and to discuss the decision with family members, friends and medical professionals. In such cases, the patient's relative or carer may act as the patient's representative and provide assent to the study procedures.

In both cases, the patient will be given the opportunity to discuss and confirm consent or opt out of the study when they are able to independently consent as assessed by the local doctor.

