9.2 Randomisation procedure

Randomisation will be via an automated 24 hour randomisation service provided by the University of Aberdeen Health Services Research Unit. The local investigator or delegated person will personally contact this service on [name] along with the trial ID code specific for each centre, known only to the randomisation centre and local investigator. During the call you will also be required to enter the patient's initials. Once this information has been submitted you will receive a randomisation code and a treatment allocation stating either "anticoagulants" or "antiplatelets." Once randomised into the study, all patients will be included in an "intention to treat" analysis.

In the unlikely event of a system failure where you are unable to contact the automated randomisation service you should call the back-up number [name] or perform a manual randomisation by flipping a coin. Please assign a treatment arm to each side of the coin and ask an independent person to flip the coin. Please retain accurate records regarding the event. If you perform a manual randomisation please contact the trial coordinator as soon as possible so that the randomisation details can be passed on to the University of Aberdeen who will update the system retrospectively.

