10.4.1 Follow up assessments

Patients will be seen for follow-up at 3 months post randomisation. Data on outcome and occurrence of recurrent stroke and TIA will be recorded. Repeat imaging with MRA, CTA or intra-arterial angiography should be performed at follow-up to assess vessel recanalisation whenever possible.

In addition, patients will be contacted via telephone at 6 months and 1 year post-randomisation by the central study co-ordinating office at St George's University of London.

To help prevent the loss of participants to follow-up and accurately measure study outcomes, the NHS Information Centre Medical Research Information Service will carry out long-term follow up of study participants. This will include providing relevant information to the Chief Investigator when the following occur during follow up:

- A participant dies
- A participants Primary Care Trust (PCT) changes

Where contact with a subject has been lost and a notification of PCT change has been received, the Chief Investigator will contact the PCT to request details of the participants new General Practitioner (GP). Subsequently the Chief Investigator will then contact the identified GP to request the contact details of the participant or that his contact details are passed onto the participant.

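### Withdrawal has only one level and ends all further data collection, so patients who would refuse only visits or calls are also lost to record-based follow-up

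*Protocol*

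**What the plan says.** Section 10.8.1 sets out the only route out of the study, "Patients will only be withdrawn from the study if consent is withdrawn", and its consequence, "In this circumstance no follow-up data will be collected". No intermediate level is described.

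Other parts of the protocol bear on this rule:

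- Section 9.1 tells patients that "they can withdraw at any time during the trial, without having to give a reason". Patients entered by witnessed consent, or on the assent of a relative or carer, are later to be able to "confirm consent or opt out of the study when they are able to independently consent".
- Section 9.2 commits to intention to treat: "Once randomised into the study, all patients will be included in an" analysis of that kind. Section 15.1 repeats the principle.
- The next paragraph of section 10.8.1 says of patients later found to have no dissection that "the patient should still have all follow-up visits and calls as this is an intention to treat study".
- Section 10.4.1 arranges that "the NHS Information Centre Medical Research Information Service will carry out long-term follow up of study participants". The stated purpose is to limit loss to follow-up. The events to be notified are death and a change of Primary Care Trust.
- Section 6.2 continues study treatment to the three-month visit "unless the medication of choice needs to be stopped for safety reasons". Stopping drug is not listed as withdrawal from the study.
- Section 15.2.1 makes the primary endpoint ipsilateral stroke or death from any cause in the three months after randomisation.

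**The concern.** The rule treats two different decisions as one. A patient may be tired of clinic visits or telephone calls yet have no objection to the trial learning from existing records whether he or she has died or had a stroke. Section 10.8.1 gives that patient only the choice between full participation and no further data. Outcomes not collected for this reason cannot be recovered by any later analysis plan.

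Three features of this trial make the loss matter:

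- Treatment is open-label (section 4.2), so the decision to withdraw can depend on the arm.
- Patients entered on a relative's or carer's assent were too unwell in the acute phase to decide for themselves. Their chance to opt out comes after randomisation, so any loss there may be related to severity.
- Section 15.3.1 says that the proportion with endpoints over three months will drive the sample size of the definitive trial. If events are few, a handful of unknown outcomes weighs heavily on that proportion.

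**Working it through.** **Reading the sections together.** There is no stated figure to reproduce, because the point concerns a conduct rule.

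1. Section 10.8.1 keeps patients without dissection in full follow-up for the sake of intention to treat. In the same section, withdrawn patients have no further follow-up of any kind, whatever they would have agreed to.
2. Death is half of the primary composite, and section 10.4.1 already sets up a passive source for it. The withdrawal rule closes that source even to patients who would allow its use.
3. That source, as described, reports deaths and changes of Primary Care Trust. Ipsilateral stroke, the other half of the composite, would have to come from medical or GP records.
4. The rule acts forward only. Nothing in section 10.8.1 says that data already collected are deleted or left out, and the Kaplan-Meier analysis of section 15.1 can use time up to withdrawal. Censoring there is unbiased only if withdrawal is unrelated to risk, which is open to doubt for the reasons given above.

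**Illustration of size.** Inputs:

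- N = 250 (section 15.3.1).
- Observed events e and withdrawals w are both assumed, as the protocol gives neither.

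If no withdrawn patient had a later event, the proportion is e/N. If every one did, it is (e + w)/N.

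| Events e (assumed) | Withdrawals w (assumed) | Lower bound e/250 | Upper bound (e + w)/250 |
|---|---|---|---|
| 5 | 2 | 2.0% | 7/250 = 2.8% |
| 5 | 5 | 2.0% | 10/250 = 4.0% |
| 5 | 12 | 2.0% | 17/250 = 6.8% |
| 12 | 2 | 4.8% | 14/250 = 5.6% |
| 12 | 5 | 4.8% | 17/250 = 6.8% |
| 12 | 12 | 4.8% | 24/250 = 9.6% |

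For comparison, the exact (Clopper-Pearson) 95% interval with no withdrawals is 0.7% to 4.6% for 5/250 and 2.5% to 8.2% for 12/250. With 2 or 5 withdrawals the worst case therefore stays inside the sampling interval. With 12 it goes beyond it (6.8% against 4.6%, and 9.6% against 8.2%).

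By arm, 1:1 allocation gives about 250/2 = 125 patients each. If 5 withdrawals all fell in one arm, the worst-case shift in that arm would be 5/125 = 4.0 percentage points.

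**The case against.** The strongest reply is that ending data collection when consent is withdrawn respects the patient, and that every trial with a right to withdraw has some missing outcomes. That is correct. Honouring a full withdrawal is not an error, and the point does not ask for it to be overridden. It asks only that a patient who would accept less than full withdrawal be offered that choice.

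Several stronger readings are tempting but not supported:

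- A reader might infer that withdrawn patients lose all their outcome data. The sentence stops future collection only.
- A reader might infer that intention to treat cannot be kept at all. A withdrawn patient can still be analysed in the allocated arm, with time up to withdrawal. The analysis is weakened by missing outcomes, but it is not abandoned.
- A reader might infer that patients harmed by their treatment are lost. Sections 6.2 and 10.8.1 let a patient stop drug for safety and remain in follow-up, so the commoner threat is already met.
- A reader might infer that NHS notification would restore the primary endpoint. It would supply deaths but not strokes.
- A reader might take the upper bounds as likely values. They require every withdrawn patient to have an event, and both counts are assumed. For 5/250, sampling error alone already covers 2.0% to 4.0%, so the bounds do not show that this rule would change the decision on a definitive trial.

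Two further objections stand in part. Section 4.1 reports that most recurrent events come in the first month, so a late withdrawal loses little; an early one or an early opt-out could lose more. Censoring and the reporting of withdrawals by arm are commonly left to the statistical analysis plan, which is not at hand, so their absence is no finding. The rule on what may be collected is different, because the protocol itself fixes it.

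**Conclusion.** The point holds as a modest, inexpensive improvement. Section 10.8.1 states an all-or-nothing rule which, followed exactly, gives up later outcomes from patients who might have agreed to record-based follow-up. It sits badly with the intention-to-treat commitment in sections 9.2 and 15.1, with any-cause death in the primary endpoint, and with the death notification arranged in section 10.4.1.

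The size cannot be fixed from the documents. With 5 events in 250, 2 withdrawals move the worst case only to 2.8% and 5 move it to 4.0%. Only at about 12 withdrawals does the worst case pass the exact confidence limit.

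Two assumptions remain: that some withdrawing patients would accept passive follow-up, and that their outcomes may differ from those of patients who stay. Neither can be tested here. The consent pages are not available, so whether patients were asked about use of records after withdrawal is also unknown.

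**What to change.** Replace the sentence on follow-up data in section 10.8.1 with two levels, each chosen by the patient and recorded:

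1. No further visits or calls, but outcome data may be taken from existing medical and GP records and from NHS death notification.
2. Withdrawal from all further data collection.

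In the same place, state that data collected up to withdrawal are kept and analysed in the allocated arm. Apply the same two levels to patients who opt out under section 9.1 after witnessed consent or after a relative's or carer's assent, and cross-refer to section 10.4.1.

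The cost is an ethics amendment to the protocol, the consent form and the Drop Out Form named in section 6.4. There is also a small amount of new work: section 10.4.1 approaches GPs only for contact details, so strokes would have to be looked up in records and passed to the adjudication committee. Outcomes of patients who choose the second level will remain unknown, and that is accepted.

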11.1 Name and description of each IMP

The CADISS Study is comparing two well known therapies: antiplatelet treatment and anticoagulation. The drugs used will include:

(a) Antiplatelet IMPs: Aspirin, dipyridamole or clopidogrel alone or in dual combination.

(b) Anticoagulation IMPs: Heparin (either unfractionated heparin or a therapeutic dose of low molecular weight heparin namely dalteparin, enoxparin and tinzaparin) followed by warfarin aiming for an INR in the range 2-3.

11.2 Source of IMPs including placebo

All IMPs will be sourced from routine hospital stock and their handling and management will be subject to standard procedures of the pharmacy'.

11.3 Accountability procedures for the IMP(s)

IMP labelling will not be applied to any antiplatelet or anticoagulant as their use falls under the remit of Regulation 46(2) of the Medicines for Human Use (Clinical Trials) Regulations, for the following reasons:

1) The IMPs are marketed products, used broadly within their authorisations (Ischemic stroke and TIA.)

2) The IMPs will be dispensed to subjects in accordance with a prescription given by an authorised health care professional.

3) The IMPs will be labelled in accordance with the requirements of Schedule 5 to the Medicines for Human Use (Marketing Authorisations Etc.) Regulations 1994 that apply in relation to dispensed relevant medicinal products.

A member of the study team should always try, where possible, to document the batch number of the medication given to any CADISS patient. This is to allow transparency when SUSARs are reported to the CADISS coordinating centres.

11.4 Route of administration, dosage, dosage regimen, and treatment period(s) of the IMPs

The dose and frequency of IMP should reflect local policy and NICE guidelines.

CADISS patients should be given IMP from the time of randomisation until their three month follow-up appointment. After this time, the treatment choice is at the discretion of the prescribing physician and the patient should begin taking non-IMP.

11.5 Dosage modifications

Any dose modifications (for example in the case of an SAE) are at the discretion of the prescribing physician. Any modifications should be documented in the patient's medical notes.

11.6 Assessment of compliance

Compliance will not be assessed as part of the CADISS Trial.

11.7 Post-trial IMP arrangements

Following study completion, all patient prescriptions will be at the discretion of the usual care provider.

11.8 Name and description of each non-IMP (NIMP)

There will be no NIMPs in this trial. Concomitant medication or therapy will be allowed.

Subjects may continue with any medication as prescribed by their own General Practitioner (GP); (see exclusion criteria) and these prescribed drugs will be recorded as part of their medical history. GP's will be informed about subject's trial participation with a GP letter.

The administration of all concomitant medication must be recorded in the appropriate sections of the Case Report Form (CRF).

12: Pharmacovigilance

12.1 Definitions

Adverse Event (AE)—any untoward medical occurrence in a patient or clinical trial subject who is administered an IMP and which does not necessarily have a causal relationship with this treatment. (i.e. any unfavourable or unintended change in the structure (signs), function (symptoms), or chemistry (lab data) in a subject to whom an IMP has been administered, including occurrences unrelated to that product)

Adverse Reaction (AR)—any untoward and unintended responses to an IMP related to any dose administered. (i.e. any unfavourable or unintended change in the structure (signs), function (symptoms), or chemistry (lab data) in a subject to whom an IMP has been administered and related to any dose administered)

Serious Adverse Event (SAE) or Serious Adverse Reaction (SAR)—any Adverse Event or Reaction in a trial subject that:

- Results in death; or
- Is life-threatening (places the subject, in the view of the Investigator, at immediate risk of death)
- Requires hospitalisation or prolongation of existing hospitalisation (hospitalisation is defined as an inpatient admission, regardless of length of stay; even if it is a precautionary measure for observation; including hospitalisation for an elective procedure, for a pre-existing condition)
- Results in persistent or significant disability or incapacity (substantial disruption of one's ability to conduct normal life functions)
- Consists of a congenital anomaly or birth defect (in offspring of subjects or their parents taking the IMP regardless of time of diagnosis).

Important medical events that may not be immediately life-threatening or result in death or hospitalisation but may jeopardise the subject or may require intervention to prevent one of the outcomes listed in the definition of serious will also be considered serious.

Suspected Unexpected Serious Adverse Reaction (SUSAR)—an Adverse Reaction which is classed in nature as both serious and unexpected.

An Unexpected Adverse Reaction is an Adverse Reaction, when both the nature and severity of the event is not consistent with the information about the medicinal product in question, as set out below:

- (a) in the case of a product with a marketing authorization, in the Summary of Product Characteristics (SmPC) for that product,
- (b) in the case of any other IMP, in the Investigator's Brochure relating to the trial in question.

12.2 Recording Adverse Events (AEs)

All Adverse Events will be recorded in the hospital notes. This information will not be collected centrally as CADISS is a Phase IV trial of licensed medications with well established safety profiles and all drugs are being used within their licensed dose and indication.

12.3 Procedures for recording and reporting SAEs

For the purposes of the CADISS Study we will only be collecting information on the following:

- **SAEs of interest:** TIA, Stroke, any major bleeding, presence of residual stenosis at 3 months (>50%) and any patient deaths.
- **Any SUSAR.** Please ensure you refer to the IMP reference documents including the SmPC used locally and the BNF website (www.bnf.orh.uk) to assess the expectedness of the SAE in relation to the IMP.

The following descriptions will be used to record SAEs:

Clinical symptoms—a simple and brief description.

Severity will be described using the following categories:

Mild—the adverse event does not interfere with the volunteer's daily routine, and does not require intervention; it causes slight discomfort.

Moderate—the adverse event interferes with some aspects of the volunteer's routine, or requires intervention, but is not damaging to health; it causes moderate discomfort.

Severe—the adverse event results in alteration, discomfort or disability which is clearly damaging to health.

Relationship to treatment—the assessment of relationship of AEs to the administration of IMP is a clinical decision based on all available information at the time of the completion of the CRF. The following categories will be used:

Definitely—there is clear evidence to suggest a causal relationship, and other possible contributing factors can be ruled out.

Probably—there is evidence to suggest a causal relationship, and the influence of other factors is unlikely.

Possibly—there is some evidence to suggest a causal relationship (e.g. the event occurred within a reasonable time after administration of the trial medication). However, the influence of other factors may have contributed to the event (i.e. the patient's clinical condition, other concomitant events).

Unlikely—there is little evidence to suggest there is a causal relationship (e.g. the event did not occur within a reasonable time after administration of the trial medication). There is another reasonable explanation for the event (e.g. the patient's clinical condition, other concomitant treatments).

Not related—there is no evidence of any causal relationship.

Not Assessable

Expectedness will be described using following categories:

Expected—an AE that is classed in nature as serious and which is consistent with the information about the IMP listed in the Investigator Brochure (or SmPC) **or clearly defined in this protocol.**

Unexpected—an AE that is classed in nature as serious and which is not consistent with the information about the IMP listed in the Investigator Brochure (or SmPC).

All SAEs will be recorded in the hospital notes and the CRF, and the Sponsor's SAE Recording Log. The SAE Log will be sent to Sponsor on request and every 2 months.

- All SAEs, SARs and SUSARs should be recorded on the SAE reporting form. Within **24 hours** of learning of a **SAE, SAE or SUSAR**, it should be reported to the CADISS Trial Office using the following [contact]** or email address: [contact].
- All SAEs will be reported to the Sponsor via the JRO on an SAE form unless otherwise stated in the protocol. The Chief or Principal Investigator will complete the Sponsor's SAE form and the form will be faxed to the JRO on [name] or E-mailed to [contact], within 24hrs of the Investigator becoming aware of the event.

The Chief or Principal Investigator will respond to any SAE queries raised by the Sponsor as soon as possible.

All SUSARs will be notified to the Sponsor immediately or at least within 24hrs of the Investigator becoming aware of the event.

